## **9.4 Complaint Handling**

On-site complaints will be handled by the study investigators, [name], [name], [name], and her research staff professionally. If a complaint raised cannot be adequately managed by the available personnel, a consensus will be reached in a meeting held at the end of the test day with other involved members to manage the issue as soon as possible.

A complete follow-up report will be prepared within 8 additional calendar days to be disseminated to all members of the research project. Electronic copies of the report with identifiable participant information will be kept on a secure website or password-protected computer with access limited to [name], [name], [name] and her research staff.

# **10. DATA ANALYSIS**

## **10.1 Data Quality Assurance**

To ensure a reliable execution of the study protocol, compliance with the diet interventions will be promoted by frequent online and in-person contact, food records as well as photographs of the subject's meals which will be sent to the study personnel for regular checks on pre-determined dates. Any biases will also be minimised by blinding of the study investigator and outcome assessors.

Analytical accuracy and validity will be maintained by ensuring that all involved personnel are properly briefed and trained prior to commencing any analysis. Complete data entry will occur within one week of data collection. A random 10% of all observations will be double entered weekly. A data entry error rate exceeding 1% will prompt a review of data entry and coding procedures and double entry of all data since the last data review. The distributional characteristics of each dependent variable will be assessed and the data transformed as needed if the assumption of normality is violated.

## **10.2 Data Entry and Storage**

Subjects will be assigned a subject ID, with the link between their subject ID and name kept separate from the data. Personal identifiers to be collected include the participant's name, email address and contact number. The linkage between subjects' personal identifiers and data will be stored both on paper and electronically on password-protected computers belonging to the Co-Investigator, [name]. Data stored on paper and the computers will be kept in [name] office, with access code required for entry.

In summary, data from on-site health assessments including anthropometric, blood pressure and skin carotenoid status as well as medical and diet logs will first be recorded on paper. The original paper copies of all identifiable data will be kept in locked storage cabinets and rooms with access limited to [name], [name], [name] her research staff. Subsequently, all research entries will be collated for storage electronically. Electronic copies of the data with identifiable participant information will be kept on a secure website with access limited to [name], [name], [name] and her research staff. All data will be de-identified prior to statistical analyses. There will be scheduled changes to passwords. There will be encryption of all email or protection by password of all data with personal identifiers.

## **11. SAMPLE SIZE AND STATISTICAL METHODS**

### **11.1 Determination of Sample Size**

Outcomes of interests in this research include the difference in plasma zeaxanthin and MDA concentrations. Previous research reported that the plasma zeaxanthin concentration was significantly increased after consuming 15 g/day of wolfberry for 28 days ( $0.058 \pm 0.011 \mu\text{mol/L}$ , mean  $\pm$  SEM) compared to not consuming wolfberry ( $0.006 \pm 0.003 \mu\text{mol/L}$ , mean  $\pm$  SEM) (31). For the current study, presuming the proposed experiment yields similar results as previously,  $\geq 12$  participants per group will provide  $\geq 95\%$  power at  $\alpha = 0.05$  (two-tailed) to statistically confirm a similar difference. Also, recent research reported that the plasma MDA concentration was decreased after consuming 14 g/day of wolfberry with meal for 45 days ( $-3 \pm 1 \mu\text{mol/mg}$  of protein, mean  $\pm$  SEM) compared to not consuming wolfberry ( $3 \pm 1 \mu\text{mol/mg}$  of protein, mean  $\pm$  SEM) (32). For the current study, presuming the proposed experiment yields similar results as previously,  $\geq 20$  participants per group will provide  $\geq 95\%$  power at  $\alpha = 0.05$  (two-tailed) to statistically confirm a similar difference.

Although the primary outcome of this research is the difference of endothelial function after consuming a healthy eating pattern diet with wolfberry versus a same diet without wolfberry, power calculations based on endothelial function-related parameters were not done due to the lack of preliminary data. As such, the endothelial function-related responses in the current study will be used to calculate effect sizes for future research.

## **11.2 Statistical and Analytical Plans**

The main effects of meal, time, and their interactions on the dependent variables will be determined by repeated-measures analysis of variance (ANOVA). All analyses will be performed in SAS 9.4 (SAS Institute Inc., Cary, NC) and results will be expressed as mean  $\pm$  SE, otherwise noted, and statistical significance will be accepted at  $p < 0.05$  (two-tailed).

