## **4. TRIAL SCHEDULE**

For this 16-week randomised, parallel-design prospective study, subjects are required to attend 6 visits including an initial screening visit. The duration for each visit is estimated to be approximately 5 hr for the pre- and post-intervention visits and approximately 2 hr for the screening and monthly visits in between. Following the initial screening visit, each visit would be separated by a 4-week interval. The trial schedule is depicted in the schematic attached in Appendix 1.

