### **6.3.2 Study Visits and Procedures**

Prior to each visit, subjects will be required to fast from the night before for approximately 10 to 12 hrs.

The following procedures will be conducted by trained research staff on the pre- and post-

intervention visits:

1. Sampling of fasting-state blood (60 mL) through intravenous cannulation from one of the subject's arms in a room at NUH IMU designated and approved for phlebotomy purposes.
2. Anthropometric measurements including height (pre-intervention visit only), weight and waist circumference at Food Science & Technology Programme, NUS.
3. Blood pressure measurement at Food Science & Technology Programme, NUS.
4. Skin carotenoid status analysis using resonance Raman spectroscopy at Food Science & Technology Programme, NUS.
5. Endothelial-dependent brachial artery FMD and carotid IMT using high-frequency ultrasonographic imaging at the National University Heart Centre
6. Body composition assay by DXA at the Orthopaedic Diagnostic Centre, NUHS
7. Questionnaires and assessment forms including a 3-day food record, Pittsburgh sleep quality index questionnaire, sleep evaluation questionnaire, perceived stress questionnaire, Montreal cognitive assessment, subjective appetite visual analogue scale and quantitative food frequency questionnaire (FFQ: pre-intervention visit only) at Food Science & Technology Programme, NUS.

The following procedures will be conducted by trained research staff on the three visits in between:

1. Sampling of fasting-state blood (20 mL) through intravenous cannulation from one of the subject's arms in a room at NUS OHC designated and approved for phlebotomy purposes.
2. Anthropometric measurements including weight and waist circumference at Food Science & Technology Programme, NUS.
3. Blood pressure measurement at Food Science & Technology Programme, NUS.
4. Skin carotenoid status analysis using resonance Raman Spectroscopy at Food Science & Technology Programme, NUS.
5. Questionnaires and assessment forms including a 3-day food record, Pittsburgh sleep quality index questionnaire and subjective appetite visual analogue scale at Food Science & Technology Programme, NUS.

The collected blood samples will be stored and analysed for the following parameters :

1. Blood lipid-lipoprotein concentrations: Total cholesterol, high-density lipoprotein

cholesterol, low-density lipoprotein cholesterol, and total triglyceride (every 4 weeks).

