2. Blood carotenoid concentration: Fasting state lutein, zeaxanthin, lycopene,  $\alpha$ -carotene,  $\beta$ -carotene,  $\alpha$ -cryptoxanthin, and  $\beta$ -cryptoxanthin concentrations using high-performance liquid chromatography (HPLC; pre- and post-intervention only).
3. Oxidative stress and inflammatory-related parameters: Concentrations of plasma oxidative stress (malondialdehyde (MDA), glutathione peroxidase (GPX), and superoxide dismutase (SOD)) and inflammatory (tumour necrosis factor- $\alpha$ , interleukin-6, monocyte chemoattractant protein-1) biomarkers using commercially available ELISA assay kits (pre- and post-intervention only).
4. Concentrations of vasodilation and vasoconstriction-related biomarkers: nitric oxide, endothelial nitric oxide synthase, and endothelin-1 using commercially available ELISA assay kits (pre- and post-intervention only).
5. Endothelial progenitor cells will be analyzed and enumerated using flow cytometry.
6. Lipidomic profiles: The main classes of glycerophospholipids (phosphatidylcholine, phosphatidylserine, phosphatidylglycerol, phosphatidylinositol, phosphatidylserine, including lysoglycerophospholipids) and sphingolipids (sphingomyelin and ceramides) will be analysed at pre- and post-intervention by high-performance liquid chromatography couple with targeted MRM analysis on triple-quadrupole mass spectrometers (pre- and post-intervention only).
7. Additional plasma will be stored for possible further analyses.

At the end of the subject's first visit, they will also be randomised into either the intervention or control arm using SAS 9.4 software although the intervention will only begin the following week.

One-to-one dietary counselling for each subject and an instruction sheet "My Healthy Plate dietary guide" will be provided by a research dietitian and trained research staff to achieve the healthy eating pattern diet while only subjects in the wolfberry intervention group will receive a provision of 500 g dried wolfberries every 4 weeks along with specific instructions to cook and consume 15 g/day wolfberry as part of a mixed-meal. Compliance with the diet interventions will be promoted by frequent online and in-person contact, 3-day food records (every 4 weeks) as well as photographs of the subject's meals which will be sent to the study personnel for regular checks on pre-determined dates.

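### Section 11.2 does not say which ANOVA term answers the between-arm question; for pre/post outcomes, adjusting for the Visit 1 value is more precise than meal-by-time unless the pre/post correlation is about 0.94 or higher

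*Combined protocol and SAP*

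**What the plan says.** The inferential method is one sentence in section 11.2: "The main effects of meal, time, and their interactions on the dependent variables will be determined by repeated-measures analysis of variance (ANOVA". The rest of 11.2 gives the software, reporting as mean ± SE and a two-tailed 0.05 level. Section 10.1 adds only that data may be transformed. No term, visit or covariate is singled out.

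Section 6.3.2 fixes the timing. Allocation takes place at the end of the first visit, when "they will also be randomised into either the intervention or control arm using SAS 9.4 software", "although the intervention will only begin the following week". The Visit 1 value is therefore a true baseline. The pre- and post-intervention visits, and not the three in between, include "Endothelial-dependent brachial artery FMD and carotid IMT using high-frequency ultrasonographic imaging at the National University Heart Centre". MDA belongs to the "biomarkers using commercially available ELISA assay kits (pre- and post-intervention only" group. Blood carotenoids and lipidomics carry the same restriction. Blood lipids, blood pressure, weight, waist and skin carotenoids are measured at all five study visits. For EPC the section says only "Endothelial progenitor cells will be analyzed and enumerated using flow cytometry", with no visits given.

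Section 11.1 calls endothelial function the primary outcome, gives no power for it, and adds: "As such, the endothelial function-related responses in the current study will be used to calculate effect sizes for future research". It does not say which estimate will be used.

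**The concern.** All three hypotheses in section 2.2 compare a wolfberry diet with the same or a similar diet without wolfberry. With two time points, the three terms in 11.2 address different quantities, and only one of them is the full post-intervention difference between arms. If none is named in advance, the choice can be made after the data are seen, and a main effect of half the size could be carried into effect sizes for later trials. Those effect sizes are the stated use of the unpowered primary outcome.

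The second issue is efficiency. About 40 people are expected to finish. Each will have a pre-randomisation value of the pre/post outcomes, and the plan does not use it as a covariate.

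**Working it through.** **Plan's own figures.** Section 3.1: 40 completers at 20% dropout gives 40/(1 − 0.20) = 50, which matches the recruitment target. The power of at least 95% for MDA at 20 per group (section 11.1) can be neither confirmed nor refuted, because the inputs are SEMs and the size of the cited study is not given.

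**Inputs.** n = 20 per arm (section 3.1); two-sided 0.05 (section 11.2). Assumed: equal SD of 1 before and after and in both arms, and a pre/post correlation ρ varied over a range, since the documents give none. D is the true difference between arms at the post-intervention visit; the expected difference at Visit 1 is 0 by randomisation.

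**What each term estimates, with two time points.**
- Meal main effect: (0 + D)/2 = D/2; variance (2/n)(1 + ρ)/2; 38 df.
- Time: change averaged over both arms; no comparison of arms.
- Meal-by-time: D − 0 = D, identical to a t-test on change scores; variance (2/n)·2(1 − ρ); 38 df.
- ANCOVA on Visit 1: D; variance (2/n)(1 − ρ²)(37/36); 37 df. The factor 37/36 = 1 + 1/(40 − 4) is the small-sample cost of estimating the slope.

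**Ratio of 95% CI widths, ANCOVA to meal-by-time:** √[(1 + ρ)/2 × 37/36] × t(0.975, 37)/t(0.975, 38), where the t quantiles are 2.0262 and 2.0244.

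Example, ρ = 0.5. Meal-by-time: √(0.1 × 2 × 0.5) = 0.316, × 2.024 = 0.64 SD. ANCOVA: √(0.1 × 0.75 × 37/36) = 0.278, × 2.026 = 0.56 SD. Ratio 0.879.

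| ρ (assumed) | Half-width, meal-by-time (SD) | Half-width, ANCOVA (SD) | Ratio | Narrower by |
|---|---|---|---|---|
| 0 | 0.91 | 0.65 | 0.717 | 28% |
| 0.3 | 0.76 | 0.62 | 0.818 | 18% |
| 0.5 | 0.64 | 0.56 | 0.879 | 12% |
| 0.7 | 0.50 | 0.46 | 0.936 | 6% |
| 0.9 | 0.29 | 0.28 | 0.989 | 1% |

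The ratio reaches 1 at ρ = 0.94. A simulation of 20,000 trials per value of ρ gave the same ratios to within 0.001, and both estimators averaged 0.50 for a true difference of 0.50. ANCOVA gave the narrower interval in 99, 96, 85 and 52% of trials at ρ = 0.3, 0.5, 0.7 and 0.9.

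**What the choice of term does to power.** Set D so that meal-by-time has 80% power (noncentrality 2.875, so D = 2.875 × its SE: 1.08, 0.91, 0.70 and 0.41 SD at ρ = 0.3, 0.5, 0.7 and 0.9). With a noncentral t, the meal main effect then has 54, 37, 22 and 10% power, and ANCOVA has 93, 89, 85 and 81%.

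**Zeaxanthin.** The SEMs in section 11.1 have ratio k = 0.011/0.003 = 3.67. Suppose the change SDs differ that much between arms (this takes equal group sizes in the cited study and extra spread unrelated to baseline). The ratio of SEs is then √{[1 − (1 − ρ)/(1 + k²)] × 37/36} = 0.989, 0.996, 1.003 and 1.010 at ρ = 0.3, 0.5, 0.7 and 0.9. There is no useful gain.

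**The case against.** The case against has force on several points.

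- **Validity.** A reader might infer that the planned ANOVA is wrong or ignores baseline. The documents do not support that. Meal-by-time is unbiased and uses Visit 1 by subtraction, and the meal main effect is a valid test of no effect. What is absent is a covariate and a named contrast.
- **The intended term can be partly guessed.** Section 2.2 rules out the time effect as the answer. The MDA sizing values in 11.1 (−3 versus 3) can only be changes, which points to the interaction. Group-by-visit means would also let a reader recover the full difference. This narrows the gap, but 11.2 still states the contrast for no outcome.
- **Size of the gain.** A reader might take 18% as a ceiling. It is only the value at ρ = 0.3: the gain is larger below that and nearly vanishes at 0.9.
- **Five-visit outcomes.** A reader might extend the precision claim to lipids or blood pressure. If Visit 1 is a level of time, the interaction there is a 4-df omnibus test, so a named contrast helps interpretation. Power comparisons, however, depend on the assumed effect shape and covariance. Under compound symmetry at ρ = 0.9, with the change-score test set at 80% power, the ANOVA's own Visit 5 minus Visit 1 contrast has 81.5% against 80.9% for the adjusted contrast.
- **Scope.** A reader might want this contrast to decide every hypothesis. Lipids, blood pressure, weight and waist have no hypothesis in 2.2, and endothelial function is spread over several measures with none named as primary. Naming the contrast does not settle either matter.

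**Conclusion.** The point holds for outcomes measured pre and post only. Section 11.2 leaves the between-arm term open among three that are not interchangeable: one targets half the difference, and one does not compare the arms. The valid full-difference term is less precise than ANCOVA on a baseline that is already collected, unless ρ is about 0.94 or higher. The interval is 28% to 1% narrower over ρ = 0 to 0.9, assuming 20 completers per arm and equal variances. No gain is claimed for zeaxanthin if the arms' change SDs differ as much as its published SEMs, nor for five-visit outcomes, and no claim is made for EPC. It is not established that a halved effect would in fact be reported. This is a gap in prespecification with a nearly free gain in precision, and should be corrected before the data are analysed; it does not invalidate the plan.

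**What to change.** Add to section 11.2:

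*For outcomes measured pre and post only, the treatment effect is the wolfberry-minus-control difference at the post-intervention visit with 95% CI, estimated by ANCOVA adjusted for the Visit 1 value. Meal and time main effects are descriptive. For outcomes measured at all five visits, the reported contrast is the between-arm difference at Visit 5, adjusted for the Visit 1 value.*

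In section 11.1, say that the endothelial effect sizes for future research will be based on this adjusted difference. In section 6.3.2, state the EPC sampling visits so that EPC falls under one rule or the other.

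The wording names Visit 5 and not a week for a reason. Section 4 says "Following the initial screening visit, each visit would be separated by a 4-week interval", so Visit 5 falls 4 × 4 = 16 weeks after Visit 1, while 6.3.2 starts the intervention a week after Visit 1. Those passages need to be reconciled separately.

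Cost: a few sentences and one degree of freedom (37 instead of 38). No new data, visits or software are needed.

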### **3. STUDY POPULATION**

#### **3.1 Subject enrolment number**

Recruitment will be done by an email which will be disseminated to the student and staff population within NUS. The recruitment notice will be sent out by the NUS Food Science and Technology administrative department via the NUS email and IVLE portal. In addition, validated posters will also be put up within the campus compounds on areas granted for poster pasting as well as on bulletin boards at neighbourhood void decks and community centres within the vicinity of NUH. A targeted fifty middle-aged and older men and women (aged 50 to 75 years, approximately half men and half women) will be recruited with the expectation that  $\geq 40$  subjects ( $\geq 20$  subjects per group) will complete the study ( $\leq 20\%$  dropout rate).

All participants who meet the inclusion criteria stipulated in *Section 3.3* may be enrolled for the study. There will be no restrictions based on gender or race but subjects will need to be adequately equipped with English literacy since the study material provided will be in printed in English only. Research material in other languages is unavailable due to the limitations in capability to translate all the documents effectively.

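### Five-visit outcomes: repeated-measures ANOVA has no sphericity correction or missing-visit rule; a fully specified mixed model is a cheap improvement

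*Combined protocol and SAP*

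**What the plan says.** Section 11.2 gives one method for all outcomes: the main effects of meal and time and "their interactions on the dependent variables will be determined by repeated-measures analysis of variance (ANOVA"). It adds that "All analyses will be performed in SAS 9.4" and that "statistical significance will be accepted at" p < 0.05, two-tailed. It names no SAS procedure, covariance structure, epsilon correction, missing-visit rule or analysis set. Section 10.1 deals with normality, by transformation, but not with sphericity.

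Section 6.3.2 schedules several outcomes at all five measurement visits. Lipids run through "low-density lipoprotein cholesterol, and total triglyceride (every 4 weeks"). The list introduced by "The following procedures will be conducted by trained research staff on the three visits in between" repeats weight, waist, blood pressure and skin carotenoids, together with the sleep-quality index and the appetite scale. Skin carotenoids appear in Hypothesis 3 (Section 2.2).

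Section 3.1 anticipates attrition: "A targeted fifty middle-aged and older men and women" are to be enrolled so that at least 40 (at least 20 "subjects per group) will complete the study", a dropout of 20% or less. Subjects are not replaced (Section 3.6), no follow-up is required after withdrawal (Section 6.3.4), and a withdrawn subject's data may be discarded unless otherwise agreed (Section 3.5).

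**The concern.** Two properties of classical repeated-measures ANOVA fit this design poorly.

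- **Complete vectors.** The classical routine needs all five values. A subject who leaves after Visit 4, or who misses one in-between visit, contributes nothing to that outcome. Precision is lost. The estimate is also open to bias if leaving depends on earlier measured values. That is plausible here: Section 3.5 lists newly prescribed antihypertensive or cholesterol-lowering medication as a withdrawal criterion, and blood pressure and lipids are themselves five-visit outcomes.
- **Sphericity.** The univariate F test for arm-by-visit assumes that all between-visit differences have the same variance. Measurements four weeks apart are often more alike when they are closer in time. The assumption then fails, and the uncorrected test rejects too often.

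At stake are the error rate and precision of the five-visit outcomes. The choice of contrast and baseline adjustment are separate matters.

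**Working it through.** **Inputs.** From the documents: 50 enrolled, at most 20% dropout, at least 20 completers per group (Section 3.1); five measurement visits (Sections 5.1 and 6.3.2); two-sided 5% (Section 11.2). Assumed, because the documents do not say: 1:1 allocation, dropout at random and spread evenly over the four intervals, and the between-visit correlations below.

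**1. The plan's own figure.** 50 × (1 − 0.20) = 40, or 20 per arm. Reproduced.

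**2. Error of the uncorrected arm-by-visit test.** With 20 per arm and k = 5 visits, the degrees of freedom are k − 1 = 4 and 4 × (40 − 2) = 152. Departure from sphericity is ε = [tr(A)]² / [(k − 1) tr(A²)], where A = CΣC and C = I − J/5. Simulated trials with no treatment effect (20,000 in the main run) gave:

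| Correlation | ε | Uncorrected F(4,152) |
|---|---|---|
| AR(1) 0.6 | 0.75 | 6.4-6.8% |
| AR(1) 0.7 | 0.69 | 7.0% |
| AR(1) 0.8 | 0.63 | 7.3% |
| AR(1) 0.9 | 0.58 | 7.9-8.0% |
| Compound symmetry | 1.00 | 5.0-5.2% |

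Ranges are over repeat runs. Under AR(1), Greenhouse-Geisser correction brings the rate to 4.2-5.1%.

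**3. Precision lost by complete-case analysis.** For a contrast c, the complete-case variance is c′Σc × (1/20 + 1/20). The likelihood variance is 2 × c′I⁻¹c, where I sums n × Σ⁻¹ over the visit patterns in one arm: 20 subjects with five visits, and 5/4 = 1.25 subjects each ending at Visits 1, 2, 3 and 4. The SE ratio cannot exceed √(50/40) = 1.118. Ratios of complete-case to likelihood SE, at correlations 0.6, 0.7 and 0.8:

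| Contrast | AR(1) | Exchangeable |
|---|---|---|
| Mean of Visits 2-5 minus Visit 1 | 1.087, 1.083, 1.079 | 1.081, 1.079, 1.076 |
| Visit 5 minus Visit 1 | 1.056, 1.055, 1.052 | 1.034, 1.032, 1.030 |

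If 5% or 10% of in-between visits were also missed (no document gives a rate), complete vectors fall to 40 × 0.95³ = 34.3 or 40 × 0.90³ = 29.2. The excess becomes 16-17% or 25-27% for the first contrast, and 11-14% or 21-24% for the second.

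If every withdrawn subject's data were discarded, the first contrast's ratio is 1.00 with no missed visits, about 1.08 at 5% missed and about 1.16-1.17 at 10%.

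**4. Interval width, Visit 5 minus Visit 1, AR(1) 0.7.**
- True variance of the within-subject difference: 2(1 − 0.7⁴) = 1.520. The t interval on completers' own differences has half-width 2.024 × √(1.520 × 2/20) = 0.789 (simulated 0.783).
- The pooled ANOVA error uses the mean correlation (4×0.7 + 3×0.49 + 2×0.343 + 0.2401)/10 = 0.520. Its variance is 2(1 − 0.520) = 0.961 and its half-width 1.976 × √(0.961/10) = 0.612 (simulated 0.611). This is too short: its simulated error is 11.7%.
- Mixed model, unstructured with Kenward-Roger, all observed data: simulated 0.742. That is 0.742/0.783 = 0.95 of the valid complete-case interval and 0.742/0.611 = 1.21 of the pooled one.

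Over six covariances (25 per arm, five dropouts per arm, 3,000 runs each), the mixed-model interval was 3-5% shorter than the completers' contrast interval. Against the pooled interval it was 12-30% longer where sphericity failed; the pooled interval's error was then 8.5-14.4%. With no dropout, the ratio to the completers' interval was 1.00.

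**5. Which mixed model.** Arm-by-visit error was 4.8-5.4% for unstructured covariance with Kenward-Roger, 6.4-7.7% for the same model with default degrees of freedom, and 6.0-7.6% for a random-intercept model under AR(1) 0.5-0.85.

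**6. Two-visit outcomes.** Sphericity holds automatically. The squared SE ratio, mixed to complete-case, is [(1 − r²)/20 + r²/25 + 1/25 − 2r/25] / [2(1 − r)/20]. At r = 0.3 this is 0.0651/0.0700 = 0.930, so the ratio is 0.964; at r = 0.9 it is 0.995.

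**The case against.** Several points on the other side are sound.

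- **Listwise deletion is inferred.** No section says that incomplete subjects are excluded, and SAS 9.4 is named without a procedure. The label could cover a mixed-model implementation. This stands. The documents support saying that the classical form would drop these subjects and that nothing rules that form out.
- **Greenhouse-Geisser alone repairs the error rate.** It does, but it neither recovers partial data nor addresses dropout related to earlier values.
- **The precision gain depends on keeping partial data.** Section 3.5 lets withdrawn subjects' data be discarded. If all are discarded and no in-between visit is missed, nothing is gained.
- **Sphericity failure is assumed.** Under compound symmetry there is essentially no excess error.
- **The GLS ratios treat the covariance as known.** The remedy must estimate 5 × 6/2 = 15 covariance parameters. The simulation did estimate them, and a 3-5% gain in interval width remained.

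A reader might go further and infer that any mixed model gives shorter intervals and a 5% error. The working does not bear this out. Where sphericity fails, the valid interval is longer than the pooled ANOVA interval, and a random-intercept model or default degrees of freedom leaves the error at 6-8%.

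**Conclusion.** The point holds as a cheap improvement for the five-visit outcomes. The uncorrected arm-by-visit test has about 6.4-8% error if correlation is AR(1) 0.6-0.9, and about 5% under compound symmetry. At 20% dropout with no missed in-between visits, complete-case analysis inflates the SE by about 8% for the mean of Visits 2-5 minus Visit 1, and by 3-6% for Visit 5 minus Visit 1. Missed in-between visits would add to this; discarding withdrawn subjects' data would reduce or remove it. The correlations, allocation ratio, dropout pattern and any missed-visit rate are assumptions. Bias from dropout related to earlier values is possible but was not quantified.

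A reader might infer that the primary result or the sample size is undermined. The documents do not support that. Section 11.1 makes endothelial function primary. FMD and IMT are listed only at the pre- and post-intervention visits, and zeaxanthin and MDA, the sample-size outcomes, are also measured only then. For these the SE gain is about 0.5-4%. Section 6.3.2 gives no time point for endothelial progenitor cells, so they cannot be placed on either side.

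**What to change.** In Section 11.2, add for outcomes measured at Visits 1-5:

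- PROC MIXED with arm, visit and arm-by-visit, unstructured within-subject covariance and Kenward-Roger degrees of freedom.
- All available data from randomised subjects whose data may be retained under Section 3.5, with no exclusion for a missed visit. State how many subjects' data were discarded, by arm.
- A prespecified fallback covariance, such as Toeplitz, if the unstructured model does not converge. A random-intercept fallback would bring back the excess error.
- If ANOVA is kept for any of these outcomes, the Greenhouse-Geisser p value.

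The cost is SAP wording, in the same software and with no new visits or subjects. The downside is possible non-convergence: 15 covariance parameters from about 45 subjects, the average over visits if 50 falls evenly to 40, (50 + 47.5 + 45 + 42.5 + 40)/5 = 45.
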